- Screening period
 - +/- 28-day washout period (if needed); *this can be part of the Run-in period if the Run-in period is applicable*
 - Screening period (up to 28 days). Patients will be evaluated for eligibility based on the inclusion and exclusion criteria
- Double-blind treatment period (52 weeks)
- Follow-up period (4 weeks)
- In addition, the sponsor will offer the possibility to the patients to receive pirfenidone within the study protocol after the Follow-up visit at week 56 for up to 11 months safety follow-up. During this time, the patients should be evaluated by the treating physician approximately every three months.

At the start of Screening, patients will have been on oral pirfenidone taken TID for at least 12 weeks, and the dose will have been in the range of 1602 to 2403 mg/day, for at least 4 weeks prior to the first Screening Visit. It is expected that the dose will remain within the range of 1602 to 2403 mg/day throughout the study and in accordance with the product label. In addition, in the 4 weeks prior to the first Screening Visit, patients must not have experienced either a new or ongoing adverse event of National Cancer Institute Common Terminology Criteria for Adverse Events (NCI CTCAE) version 4.03, which is Grade 2 or higher and considered, by the Investigator to be related to pirfenidone, or have had an interruption of pirfenidone treatment of >7 days for any reason.

During Screening, patients may return for the Baseline visit (Day 1) as soon as eligibility has been confirmed.

Patients who meet all eligibility criteria and who provide written, informed consent will be randomized 1:1 to receive 1 year (52 weeks) of treatment with either oral sildenafil (20 mg) or matching placebo TID while continuing to take pirfenidone. Treatment with sildenafil should be initiated and monitored by a physician experienced in the treatment of PAH.

[figure not shown]
Approximately 176 patients will be enrolled at approximately 75 study centers in Canada, Europe (EU) and Eastern Europe, Middle East, and Africa (EEMEA), *and potentially Asia-Pacific*. No replacements will be made.

Patients who experience a primary endpoint (a decline in 6MWD as defined per protocol or an event of respiratory-related non-elective hospitalization) will continue treatment and be encouraged to complete the study.

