4.5.15 Patient Study Discontinuation

Patients have the right to voluntarily withdraw from the study at any time for any reason. In addition, the Investigator has the right to withdraw a patient from study at any time. Reasons for withdrawal from the study may include, but are not limited to, the following:

- Patient withdrawal of consent at any time
- Any medical condition that the Investigator or Sponsor determines may jeopardize the patient's safety if he or she continues in the study
- Lung transplantation
- Investigator or Sponsor determines it is in the best interest of the patient

Every attempt should be made to keep patients on study treatment throughout the duration of the trial.

Every effort should be made to obtain information on patients who withdraw from the study. The primary reason for withdrawal from the study should be documented on the appropriate eCRF. However, patients will not be followed for any reason after consent has been withdrawn. Patients who withdraw from the study will not be replaced.

The Investigator should show due diligence and explore all possible options to reach a patient who fails to attend a visit. The site must document all attempts to contact the patient in the medical records / source documents.

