4.5.16 Patient Study Treatment Discontinuation

Patients must discontinue study treatment (sildenafil and/or pirfenidone) if they experience any of the following (see also [Sections 5.1.1](#) and [5.1.2](#)):

- Inability to tolerate study treatment after efforts have been made to gain tolerability
- An elevation in liver test results of the magnitude described below
- Use of a prohibited investigational therapy or concomitant medication
- Sildenafil/placebo will be stopped in patients with acute coronary syndromes, atrioventricular AV block, life-threatening arrhythmias, left ventricular dysfunction (ejection fraction <25%), or clinically significant visual changes
- Pregnancy
- Signs or symptoms of angioedema
- Any other treatment-emergent adverse event or toxicity that is unacceptable in the opinion of the patient or Investigator

Sildenafil/placebo will be stopped (temporarily or permanently) in any patient with systolic blood pressure (SBP) <100 mmHg or diastolic blood pressure (DBP) <50 mmHg.

The primary reason for study treatment discontinuation should be documented on the appropriate eCRF. Patients who discontinue study treatment prematurely will not be replaced.

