6.4.1 Primary Efficacy Endpoint

The primary efficacy objective for this study is to evaluate the efficacy of adding sildenafil compared with placebo to pirfenidone treatment in patients with advanced IPF and *risk* of Group 3 PH.

The primary efficacy endpoint will be evaluated based on a comparison of the proportion of patients showing disease progression over 52 weeks of treatment period, as evidenced by reaching the following combined endpoint:

- Relative decline in 6MWD of at least 15% from baseline (as defined below*), respiratory-related non-elective hospitalization, or all-cause mortality

* Relevant decline in 6MWD from baseline is defined as:

- Any decline >25% from baseline or
- A decline between 15-25% from baseline, if accompanied by at least one of the following:
 - worsening of SpO₂ desaturation during the 6MWT compared to baseline

- worsening of the maximum Borg scale during the 6MWT compared to baseline
- increased O₂ requirements during the 6MWT compared to baseline.

The primary analysis will be based on the ITT population, defined as all randomized patients. Patients who discontinue treatment prematurely will be analyzed based on the available data. No imputation method will be applied. Patients who undergo lung transplantation during the study will be withdrawn from the study at the time of hospitalization for transplantation. *In addition, sensitivity analysis of the primary endpoint will be performed. The details of those analyses will be provided in the Statistical Analysis Plan.*

The primary analysis of the primary endpoint will compare disease progression rates in each treatment arm using a Chi-square test with a one-sided significance level $\alpha = 0.05$.

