			-57 to -29	28 to -1	1 W1	22 W3	45 W6	90 W12	135 W19	180 W26	225 W32	270 W39	315 W45	365 W52			
(Window, days)					(±5)	(±5)	(±5)	(±5)	(±5)	(±5)	(±5)	(±5)	(±5)	(±5)	(±5)		
Treatment Period Visit					1	2	3	4	5	6	7	8	9	10			Approx. every 3 months
Spirometry post broncho- dilator (FVC, FEV1, FEV1/ FVC) ^d		X	X ^{d1}			X			X		X		X				
DLCO ^e		X	X ^{e1}			X		X		X		X		X			
6MWT and SpO ₂ (resting, nadir, and end of test) ^f		X	X ^f		X	X			X			X		X			
Borg scale		X	X		X	X			X		X		X		X		
WHO Functional Class		X	X	X	X	X	X	X	X	X	X	X	X	X			
Hematology		X	X	X	X	X	X	X	X	X	X	X	X	X			
Chemistry		X	X	X	X	X	X	X	X	X	X	X	X	X			
NT-proBNP, CRP, aldosterone			X			X			X					X	X		
Urinalysis		X	X			X		X	X				X	X			
Urine Pregnancy Test ^g			X	X	X	X	X	X	X	X	X	X	X	X			

Pirfenidone and sildenafil—F. Hoffmann-La Roche Ltd
98/Protocol MA29957, Version 2

Appendix 1

Schedule of Assessments (cont.)

Day Week	Washout ^a	Screening ^b	Double blind Treatment										Early Study Withdrawal/ Study Treat. Discontinuation	Follow- Up	Additional safety FU ⁱ , up to 11 months		
			-57 to -29	28 to -1	1 W1	22 W3	45 W6	90 W12	135 W19	180 W26	225 W32	270 W39	315 W45	365 W52			
(Window, days					(±5)	(±5)	(±5)	(±5)	(±5)	(±5)	(±5)	(±5)	(±5)	(±5)		(±5)	
Treatment Period Visit					1	2	3	4	5	6	7	8	9	10			Approx. every 3 months
Serum Pregnancy Test		X														X	
12-lead ECG		X	X						X				X	X			
ECHO		X ^h	X ^{h1}					X					X	X			
SGRQ			X			X		X			X		X	X			
UCSD SOBQ			X			X		X			X		X	X			
Serum and plasma for optional biomarker assessment		X	X														
Blood PAXgene for optional biomarker assessment		X	X														
Blood for optional DNA biomarker assessment			X														
Concomitant Medications		X	X	X	X	X	X	X	X	X	X	X	X	X	X	X	
Adverse Events	X	X	X	X	X	X	X	X	X	X	X	X	X	X	X	X	X

Pirfenidone and sildenafil—F. Hoffmann-La Roche Ltd

99/Protocol MA29957, Version 2

Appendix 1

Schedule of Assessments (cont.)

Day Week	Washout ^a	Screening ^b	Double blind Treatment										Early Study Withdrawal/ Study Treat. Discontinua tion	Follow- Up	Additional safety FU ⁱ , up to 11 months		
			-57 to -29	28 to -1	1 W1	22 W3	45 W6	90 W12	135 W19	180 W26	225 W32	270 W39	315 W45	365 W52			
(Window, days)					(±5)	(±5)	(±5)	(±5)	(±5)	(±5)	(±5)	(±5)	(±5)	(±5)		(±5)	
Treatment Period Visit					1	2	3	4	5	6	7	8	9	10			Approx. every 3 months
Review Dosing Adherence					X	X	X	X	X	X	X	X	X	X	X		
Review Patient Diary					X	X	X	X	X	X	X	X	X	X	X	X	
Dispense/ Collect Patient Diary		X													X	X	

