- f* The 6MWT will be performed once at each visit highlighted. At Baseline, it will be performed twice and the better of the two 6MWD values will be reported. Please refer to the 6MWT Procedure Manual.
- g* If a urine pregnancy test is positive, it must be confirmed by a serum pregnancy test.
- h* ECHO assessment at screening is not required for eligible patients based on RHC criteria.
h¹ Should the ECHO at screening collect all information required at Visit 1 and the patient is eligible and randomized in ≤14 days, the screening ECHO can be used as baseline
- i* The sponsor will offer the possibility to the patients to receive pirfenidone within the study protocol up to a 11 months safety follow up. During this interval the patients should be evaluated approximately every three months.
- j* During the additional safety FU, data related to the pirfenidone administration will not be collected on the CRF.

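### Appendix 1 merges stopping treatment with leaving the study, and the protocol does not secure walk tests to Week 52 for patients who stop sildenafil/placebo but stay in the study

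*Protocol*

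**What the plan says.** Section 4.5.15 covers discontinuation from the study. Section 4.5.16 separately covers discontinuation of treatment, which may be of either drug: "Patients must discontinue study treatment (sildenafil and/or pirfenidone) if they experience any of the following". A stop of the blinded drug alone is foreseen, and it need not be final: "Sildenafil/placebo will be stopped (temporarily or permanently) in any patient with systolic blood pressure". Section 6.5 also reports withdrawal from medication and discontinuation from the study as two things.

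After a treatment stop, Section 4.5.16 asks only for the reason to be recorded and adds "Patients who discontinue study treatment prematurely will not be replaced". It says nothing about later visits.

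Appendix 1 has one column for both events, "Early Study Withdrawal/ Study Treat. Discontinuation". It stands after the Week 52 visit and is followed only by the follow-up visit and the additional safety follow-up. The numbered visits all stand under the double-blind treatment heading, and footnote f says of the walk test: "The 6MWT will be performed once at each visit highlighted". No off-treatment visits are listed.

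The primary analysis (Section 6.4.1) takes all randomized patients over 52 weeks. It provides that "Patients who discontinue treatment prematurely will be analyzed based on the available data", with no imputation.

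**The concern.** Decline in 6MWD is the one component of the primary endpoint that exists only if a test is done. Deaths and hospitalizations may come to light through other contact, but a walk decline will not. If a site reads the merged column as the last treatment-period visit for anyone who stops the blinded drug, that patient contributes no walk data afterwards, although still randomized and possibly still taking study pirfenidone.

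The SAP is not at hand, but it could not repair this: it can choose how to analyse missing walk tests, but it cannot recover tests that were never performed. Visit attendance is settled by the protocol and its Schedule.

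Two things are at stake. Lost events in both arms shrink the observed difference and cost power. If the arms stop at different rates, the comparison is also biased towards the arm with more stopping.

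**Working it through.** **Text.** Two passages encourage patients to stay in the study. Section 3.1 does so for those who reach a non-fatal primary endpoint: they "or an event of respiratory-related non-elective hospitalization) will continue treatment and be encouraged to complete the study". Section 4.2 asks that unblinded patients be retained. Neither covers a patient who stops treatment without an endpoint and without unblinding. The only explicit end of follow-up is in Section 4.5.15: "patients will not be followed for any reason after consent has been withdrawn". So the text neither ends nor secures the walk tests after a treatment stop, and the Schedule leans towards closing the patient out.

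**Planned sample size.** Inputs from Section 6.1: 72% against 54%, one-sided 5%, 80% power, 1:1. With p̄ = 0.63 and pooled variance under the null:

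n per arm = [1.645·√(2·0.63·0.37) + 0.842·√(0.72·0.28 + 0.54·0.46)]² / 0.18² = (1.123 + 0.565)² / 0.0324 = 87.9, so 88 per arm and 176 in total.

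This matches the protocol. Power at 88 per arm is 80.0%, so the 176 holds no allowance for events lost after stopping.

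**Illustration.** These are assumptions, since the protocol gives no stopping rates: constant hazard over 52 weeks; stopping at week 26 while event-free; half of the later events unseen; unseen events counted as no progression. With stopping share d of all randomized patients in an arm:

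- Observed rate = true rate − d × (risk in the second half) × 0.5.
- At a true rate of 72%, √0.28 = 52.9% are event-free at week 26, and the second-half risk is 1 − 0.529 = 0.471.
- At a true rate of 54%, √0.46 = 67.8% are event-free, and the second-half risk is 0.322.

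Rejection probability = Φ{[(p₁ − p₂)√88 − 1.645·√(2p̄(1 − p̄))] / √(p₁(1 − p₁) + p₂(1 − p₂))}.

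| Scenario | Placebo observed | Sildenafil observed | Result |
|---|---|---|---|
| No effect (72% both), 10% vs 15% stop | 0.72 − 0.10·0.471·0.5 = 69.6% | 0.72 − 0.15·0.471·0.5 = 68.5% | one-sided error 7.0% |
| No effect, 10% vs 20% stop | 69.6% | 0.72 − 0.20·0.471·0.5 = 67.3% | one-sided error 9.5% |
| Planned effect, 15% stop in both | 0.72 − 0.15·0.471·0.5 = 68.5% | 0.54 − 0.15·0.322·0.5 = 51.6% | power 74.2% |

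The shares are of all randomized patients. Among those still event-free at week 26 they are larger: 10% is 0.10/0.529 = 19%, 15% is 28% and 20% is 38%. In the power row, the sildenafil share is 0.15/0.678 = 22%.

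If placebo patients stop more, the bias reverses. With the arms swapped in the first two rows, the error falls to about 3.5% and 2.4%.

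**Range.** A cruder model lets a share d of each arm stop and a share m of all their events go unseen, whenever they occur. Power under the planned effect is then 77.6% at d = 10%, m = 25% and 58.3% at d = 30%, m = 75%. With no effect, 10% vs 20% stopping and m = 50%, the error is 12.7%. This model loses more events, because it does not require patients to be event-free when they stop.

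**The case against.** A reader might infer that a patient who stops sildenafil/placebo has no further scheduled walk test, so that a later decline cannot be seen. The protocol does not say that. A column heading names an occasion for assessments; it does not cancel later visits. Several passages point towards continued attendance: follow-up is ruled out only after withdrawal of consent, information is to be sought even on patients who leave (Section 4.5.15), unblinded patients are to be retained (Section 4.2), and treatment may be stopped temporarily and restarted (Sections 4.5.16 and 4.3.2.6). A temporary stop cannot sensibly mean close-out. All of this stands, and it limits the point to an unsecured measurement.

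A reader might also infer that such patients are counted as non-progressors and that the bias favours sildenafil. Neither is stated. Section 6.4.1 does not say how a patient with incomplete walk data enters the chi-square test. Section 4.5.16 does require stops for low blood pressure and visual changes, which the protocol links to sildenafil. But it also describes most sildenafil side effects as mild to moderate (Section 1.2.2), puts orthostatic hypotension below 2% (Section 4.3.2.3.2) and excludes hypotensive patients at entry (Section 4.1.2). More stopping on sildenafil is possible but not shown.

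Finally, the scenarios need substantial stopping among patients still at risk, and they assume that none of those patients has a later walk test. Even so, the mildest case moves the error only from 5% to 7%. In the text version of Appendix 1 the tick marks are displaced, so nothing here rests on whether the closing visit includes a walk test.

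None of this supplies the missing instruction. Sites work from the Schedule, and it treats the two events as one.

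**Conclusion.** The point holds as a gap in securing primary-endpoint data. Appendix 1 merges two events that the text keeps apart, and no passage tells sites to continue walk tests in patients who stop treatment but remain in the study. Later 6MWD declines may therefore be missed in an analysis of all randomized patients over 52 weeks.

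The size is illustrative. It rests on assumed stopping at week 26, half of later events unseen, and unseen events counted as no progression. On those terms the error is about 7 to 9.5% with 5 to 10 percentage points more stopping on sildenafil, and power is about 74% with equal 15% stopping. The direction of any bias depends on which arm stops more, which is not known. If the visits continue and the events are seen, the planned 80% stands. The change should be made because it is cheap and the lost data cannot be recovered later.

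**What to change.** - **Appendix 1:** split the column. Keep the closing visit for study withdrawal only. For treatment discontinuation, do the assessments once and then continue the remaining scheduled visits.
- **Section 4.5.16:** state that patients who stop sildenafil/placebo and/or pirfenidone, but have not withdrawn from the study, attend all remaining scheduled visits to Week 52, including the walk tests with Borg scale, SpO₂ and O₂ use.

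This concerns data collection only and changes no rule for stopping treatment. The visits and tests are already planned for every patient, so the cost is amendment wording, a change of table layout, and some visit burden for patients off treatment.
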